## 4.2.2 Other Dose Escalation/De-Escalation Procedures

The following provides a description of the procedures not directly associated with the BOIN as such, but that will impact subject accrual and provisions for dose escalation/de-escalation decisions.

- 1. After completion of the first full dosing of each DL cohort, based on the safety data and the BOIN, the sponsor SC will decide on the dose-level for the next cohort of subjects. Escalation to the next dose-level will not occur until all subjects needed for a specific DL cohort have passed the Cycle 1/DLT evaluation period.
- 2. The Dose Escalation part will be assessed in dose-level cohorts (DL cohorts); initially this will be in done in single-subject cohorts until the trigger point (see Section 4.2) is passed.
  - A single-subject DL cohort may be optionally expanded with up to 2 additional subjects for the purpose of obtaining additional safety, PK, pharmacodynamic, and biomarker data (ie, for a total of 3 subjects in that cohort).
- 3. A subject will be considered as evaluable for dose determination if they experience a DLT or meet the minimum treatment and safety evaluation requirements for the first cycle (refer to Section 7.1).

After completion of the DLT period for each DL cohort, the DEC and sponsor SC will review the data from the DLT period to propose the actual next dose level. Data to be reviewed will include but not be limited to all relevant safety, clinical, PK, biomarker data, and the next dose as suggested by the BOIN strategies.

The RP2D to be used for the Expansion part will be determined at the end of the Dose Escalation part by the DEC and sponsor SC, based on a review of the totality of data, including but not limited to efficacy, safety (including DLTs, AEs, safety laboratory values, and observations made after the end of the DLT evaluation period), biomarker and PK data, and dosing information.

## 4.3 Expansion Part

In the Expansion part, subjects will receive the RP2D dose(s) determined from the Dose Escalation part. Depending on the RP2D, this will be a priming dose of GEN1044 on C1D1, an intermediate dose on C1D8, and then either a second intermediate dose or full dose on C1D15. In case of the implementation of a second intermediate dose on C1D15, the subject will receive the first full dose on C2D1.

An overnight stay (24 hours in-hospital observation) will be required for all subjects after administration of GEN1044 on C1D1. For subjects experiencing CRS or ICANS following GEN1044 administration on C1D1, additional 24-hour hospitalization will be required after administration of GEN1044 on C1D8. As data accumulate, increased (or reduced) hospitalization

Version: 4.0

may be implemented for additional subjects and/or dose administrations if recommended by the sponsor.

Based on data available and if deemed appropriate, the expansion may be initiated before a possible maximum tolerated dose has been reached. Furthermore, different doses and schedules might be explored in the expansion cohorts. The aim of the expansion is to provide further data on the safety, tolerability, MOA, PK and anti-tumor activity of the selected dose/schedule.

Recruitment will be initiated in up to 8 parallel cohorts in different tumor types. Expansion cohorts may include disease subtypes, eg, uterine, prostate, esophageal, head and neck, NSCLC/ACC, NSCLC/SCC, bladder and TNBC. In each of the expansion cohorts, a non-binding and ongoing interim futility analysis will be conducted after about 20 subjects have at least 2 on-treatment scans (approximately 12 weeks). A maximum of 40 subjects may be recruited in each expansion cohort.

Further expansion cohorts in additional tumor types may be opened based on preliminary efficacy signals generated in the Dose Escalation part. The sponsor will determine the priority of opening the disease-specific expansion cohorts based the data obtained in the dose escalation.

In the Expansion part, a DMC risk-benefit analysis will be performed at pre-specified intervals as defined in the DMC Charter. The DMC and the sponsor SC will evaluate the safety profile with particular emphasis on any safety signals. Additional details regarding the DMC can be found in Section 10.9.

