#### 11 STATISTICS

The Statistical Analysis Plan (SAP) will be developed and finalized before database lock and will describe the subject populations to be included in the analyses, and procedures for accounting for missing, unused, and spurious data. This section is a summary of the planned statistical analyses of the primary and secondary endpoints.

All presentations will be done separately for the Dose Escalation part and the Expansion part. Subjects in the Dose Escalation part will typically be analyzed according to the assigned DL cohort. Subjects in the Expansion part will be analyzed according to their assigned expansion cohort.

The primary analyses will be timed as follows:

- **Escalation**: Primary safety and efficacy analyses will be conducted on all subject data at the end of the escalation.
- Expansion: The expansion part consists of parallel cohorts, wherein each expansion cohort may report its individual primary analysis. Primary safety and efficacy analyses will be conducted on all subject data at earliest when all subjects who are still receiving trial treatment have at least 2 scans performed (such that the primary endpoint may be confirmed).

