#### 11.6.4 Handling of Missing Values/Censoring/Discontinuations

Any subjects with missing information regarding response to treatment will be counted as non-responders. Treatment of intermediate missing scans will be detailed in the SAP.

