#### 11.6.20

# 11.7 Operating Characteristics for the Interim Analysis in Expansion Cohorts

The maximum sample size for each expansion cohort is 40 subjects. In order not to expose subjects to non-efficacious doses, an ongoing and non-binding interim futility analysis will be conducted based on about the initial 20 subjects. The interim analysis will be conducted when (at minimum) 2 scans from these subjects in the expansion cohort have been locally reviewed. At this time point the confirmed ORR will be derived and used as endpoint in the futility analysis. Those subjects not yet confirmed (eg, last scan demonstrating a CR or PR) will be counted as SD (ie, non-responders). The analysis will be supplemented by secondary summaries of the response (at timing of futility analysis): ORR (based on unconfirmed responses), DOR, anti-tumor activity (changes from baseline in target lesion size), PFS, OS, summaries of PK concentrations and parameters, and safety assessments. The totality of the data will be evaluated by the sponsor SC, which decides on further recruitment into the expansion cohort.

The futility analysis will be based on a Bayesian predictive probability approach (Lee and Liu, 2008). By using predictive probabilities, it is possible to directly assess the outcome of the next stage, if continued to its end (Saville et al., 2014). Given the interim data, the predicted probability is a weighted average of posterior probabilities, as if calculated given the outcome at the end of the stage. The weights correspond to how likely each outcome is. The predictive probabilities may in fact be calculated at any time point.

At the end of the trial the *outcome* of interest, ie, the "success criteria," is defined as the posterior probability that ORR exceeds  $p_0$  is at least 70%. If the predicted probability of success at timing of interim is less than 10% the expansion cohort is judged futile.

The historical rates  $(p_0)$  are tabulated in Table 19. Based on these, the number of responders required at interim to continue are presented by indication in Table 20. In addition, given the prior response rate, the success criteria is translated into required number of responders.

The operating characteristics are based on 100000 simulations for each scenario and were programmed in R v3.5.1 using RStudio v1.2.1335 (R-Core-Team, 2018; RStudio-Team, 2018).

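### Sections 4.3 and 11.7 define the interim 20 inconsistently and leave subjects lost before a second scan unassigned, so the futility stopping chances in Table 20 may not describe the look as written

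*Protocol*

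**What the plan says.** Protocol Section 4.3 reaches its count through scan completion: the "interim futility analysis will be conducted after about 20 subjects have at least 2 on-treatment scans", put at about 12 weeks. Section 11.7 starts from order of entry instead: an "ongoing and non-binding interim futility analysis will be conducted based on about the initial 20 subjects". It then adds a timing condition of its own: "The interim analysis will be conducted when (at minimum) 2 scans from these subjects in the expansion cohort have been locally reviewed".

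For the primary analysis, Section 11 sets a similar two-scan condition but restricts whom it applies to: "at earliest when all subjects who are still receiving trial treatment have at least 2 scans performed". The interim text has no such restriction.

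Section 11.7 does say how to treat a response not yet confirmed at the interim (as stable disease, hence a non-responder). It says nothing of a subject who never has a second scan, and it names no analysis set for the look. Section 11.6.4 gives a general rule for the expansion ORR: "Any subjects with missing information regarding response to treatment will be counted as non-responders". Section 11.1.2 keeps deaths before the first assessment in the response evaluable set as non-responders.

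**The concern.** Some subjects will have no second scan. Under Section 9.2.1.2, imaging ends at progression, new anti-cancer therapy, withdrawal of consent or death. Continued imaging after RECIST progression is optional and limited to clinically stable subjects without prostate cancer. Section 9.2.1.3 does not require further imaging of clinically unstable subjects. Early deaths, consent withdrawals, switches to new therapy, and progressors who have prostate cancer or are unstable therefore generally cannot satisfy the trigger.

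That leaves two literal outcomes. Either the look waits, because some of the initial 20 will never have two scans, or it is made on 20 subjects who each reached two scans. In the second case the 20 are selected for having stayed about 12 weeks. The interim ORR is then inflated, and cut-offs derived for unselected subjects are applied to a favourable subset. The look exists to avoid exposing subjects to doses that do not work, so what is at stake is how many subjects are treated in a cohort no better than the historical rate.

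**Working it through.** **Inputs from the Protocol.** Historical rates p0 are 10%, 15% and 35% for Cases A, B and C (Table 19). The prior is Beta(1 + p0, 2 − p0), final success is a posterior probability of at least 70% that ORR exceeds p0 at n = 40, and futility is a predictive probability of success below 10% (Section 11.7). Table 20 states the chance of not being judged successful at n = 20 as 12%, 18% and 24% when the true ORR equals p0.

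**Step 1: reproduce Table 20.** The smallest number of responders meeting the final criterion is 5, 7 and 16 of 40. The smallest interim count c with predictive probability of at least 10% is:
- A: c = 1 (0.156; with 0 responders, 0.022)
- B: c = 2 (0.185; with 1 responder, 0.041)
- C: c = 6 (0.139; with 5 responders, 0.042)

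Table 20 prints the Case A cut-off as more than 1 of 20, but its 12% corresponds to at least 1.

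With 20 unselected subjects, P(stop) = P(Bin(20, p0) ≤ c − 1):
- A: 0.90^20 = 12.2%
- B: 0.85^20 + 20 × 0.15 × 0.85^19 = 17.6%
- C: P(Bin(20, 0.35) ≤ 5) = 24.5%

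These match the stated 12%, 18% and 24% to within rounding and simulation error. Table 20 therefore describes 20 subjects taken without regard to scan completion.

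**Step 2: condition the 20 on having two scans.** Let f be the share without a second scan. The documents give no value, so f is an assumption shown over a range. Confirmed response needs a repeat image (Sections 9.2.1.2 and 11.5.10.1), so these subjects are taken to have no confirmed response. The ORR among the rest is p0/(1 − f), and P(stop) = P(Bin(20, p0/(1 − f)) ≤ c − 1). For Case A at f = 20%: 0.10/0.80 = 0.125, and 0.875^20 = 6.9%. The expected number treated to obtain 20 subjects with two scans is 20/(1 − f).

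| f (assumed) | A: ORR, P(stop) | B: ORR, P(stop) | C: ORR, P(stop) | Treated to obtain 20 |
|---|---|---|---|---|
| 0 | 10%, 12.2% | 15%, 17.6% | 35%, 24.5% | 20 |
| 10% | 11.1%, 9.5% | 16.7%, 13.0% | 38.9%, 14.8% | 22 |
| 20% | 12.5%, 6.9% | 18.8%, 8.8% | 43.8%, 6.9% | 25 |
| 30% | 14.3%, 4.6% | 21.4%, 5.2% | 50%, 2.1% | 29 |

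**Step 3: true rates below p0.** At half of p0, the chance of stopping is 36%, 55% and 88% with unselected subjects, and 28%, 43% and 74% at f = 20%. At ORR 0 it is 100% whatever f is.

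**The case against.** The best defence is that the two sections answer different questions: 4.3 says when the look happens, and 11.7 says who is in it. No sentence removes or replaces an early failure. Section 8.2 says that subjects who withdraw are not replaced, although that sentence sits in a paragraph on withdrawal of consent. Sections 11.6.4 and 11.1.2 both point towards counting early failures as non-responders. This stands in part: exclusion is a reading that the text permits, not a rule that it states. But 11.7 also requires two scans from its own 20 subjects, so separating timing from membership does not settle the trigger. The non-response rules assign an outcome to subjects already in the denominator; they do not say who is in it or when the condition is met.

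A second objection is that not every early progressor or discontinuer lacks a second scan. Clinically stable non-prostate subjects may be imaged after RECIST progression, and subjects who stop treatment without radiographic progression continue to be imaged (Sections 8.1, 9.2.1.2 and 9.2.1.3). Such later scans could satisfy 11.7, though scans after treatment has stopped would not count as the on-treatment scans that 4.3 asks for. This stands, and it narrows the affected group.

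Third, the look is non-binding, predictive probabilities may be computed at any time, and the sponsor's Safety Committee weighs all the data, including PFS and OS, where early progression and death count directly. This also stands: the figures above concern the rule, not an automatic decision.

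**Conclusion.** The point holds as an inconsistency in the definition of the interim set, with a consequence whose size depends on an early-loss share that the documents do not give. If early leavers are excluded, a 20% loss cuts the chance of stopping at p0 by about 43% in Case A (12.2% to 6.9%), by half in Case B (17.6% to 8.8%) and by about 72% in Case C (24.5% to 6.9%). About 25 to 29 subjects must be treated to obtain 20 with two scans at losses of 20% to 30%.

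A reader might infer that the rule would almost never stop an inactive cohort. The documents do not support that. Stopping chances near zero in all three cases need a loss of around 50% (1.2%, 0.8% and under 0.1%) and a true ORR exactly at p0. A cohort with ORR 0 is always flagged, and one at half of p0 is still flagged 28% to 74% of the time at a 20% loss. Nor is most of the weakness at p0 due to the scan wording: with all 20 counted, the rule stops only 12% to 24% of such cohorts, and the Protocol says so.

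No result is affected. SAP Section 2.2 records that no expansion data were collected, so this concerns the plan only.

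**What to change.** Use one definition in both 4.3 and 11.7. The interim set is the first 20 treated subjects in the cohort. The data cut-off falls when each has had two post-baseline scans or has earlier progressed, died, started new anti-cancer therapy or left the trial. All 20 stay in the denominator, and anyone without a confirmed response counts as a non-responder, consistent with 11.6.4.

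The cost is two sentences in the Protocol. No extra subjects are needed, and the look does not have to wait for scans that will never be made. The existing cut-offs and Table 20 figures then apply as stated, subject to correcting the printed Case A cut-off to at least 1 of 20.

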## 4.4 Planned Number of Subjects

- Up to approximately 80 subjects are planned to be treated in the Dose Escalation part.
- Up to approximately 320 subjects are planned to be treated in the Expansion part.
- In total, up to approximately 400 subjects are planned to be treated in the trial.
- Assuming an anticipated screen failure rate of 30%, approximately 570 subjects can be screened.

## 4.5 Trial Design Rationale

The first part of this trial is a FIH, open-label, dose escalation safety trial studying GEN1044 in subjects with different types of malignant solid tumors, to determine the safety profile of GEN1044.

In order to address the trial objectives in this FIH trial, a BOIN design was selected. Compared to standard 3+3 and accelerated titration designs, the chosen BOIN design provides more flexibility while safeguarding the subject's safety.

[figure not shown]
The second part of this trial is the expansion of tumor-specific cohorts for further investigation. The aim of the expansion is to provide further data on the safety, tolerability, PK, and anti-tumor activity of the selected dose in specific tumor types.

### 4.6 Dose and Schedule Rationale

The first-in-human (FIH) dose selection takes into account the MOA of GEN1044 (T-cell activation and T-cell mediated cytotoxicity of 5T4-expressing tumor cells through GEN1044-mediated crosslinking of CD3 and 5T4) and is based on estimation of the MABEL using in vitro nonclinical data.

Document Number: TMF-34513

Version: 4.0

## 4.6.1 Rationale for Fixed Dosing

An additional consideration for the development of GEN1044 is to initiate the FIH trial with fixed dosing instead of body weight-based dosing. A fixed dosing approach is desirable to facilitate drug preparation without the need to calculate the dose, per subject, thus lowering the potential risk of dosing errors as compared with body weight-based dosing. In addition, fixed dosing also offers several advantages over weight based-dosing including better convenience and compliance, reduction of preparation time, and a reduced amount of drug waste. There are several examples of mAb-based therapeutics that have either been developed using a fixed dosing approach, or switched from body weight-based dosing to fixed dosing either during clinical development or post-approval (Bai et al., 2012; Wang et al., 2009).

Furthermore, there is strong scientific rationale to support fixed dosing of GEN1044. Monoclonal antibodies typically distribute to the blood plasma and extracellular fluids only, which increase less than proportionally with increase in body weight, and elimination takes place via proteolytic catabolism and intracellular degradation after binding to the target. Binding to the target is not related to body weight but mainly to tumor load, target expression levels in tumors versus endogenous expression, and affinity of monoclonal antibody. In addition, intracellular degradation of monoclonal antibodies targeting antigens at the cell surface is also not likely to be body weight dependent. Minor effects of body size on distribution and elimination of monoclonal antibodies do not typically support body-size based dosing. Published simulation studies comparing the performance of a body size-based and fixed dosing for several mAbs demonstrated that PK variability is expected to be similar between fixed and body size-based dosing (Bai et al., 2012; Wang et al., 2009).

### 4.7 End of Trial Definition

The trial is considered completed when the last subject dies or withdraws from the trial. However, the maximum trial duration is 5 years after the last subject's first treatment in the trial. The sponsor will ensure post-trial treatment for ongoing trial participants with a potential treatment benefit.

Version: 4.0

#### 4.8 Treatment Discontinuation

Treatment should continue until the subject fulfills one of the treatment discontinuation criteria (see Section 8.1).

#### 4.9 Trial Termination

The sponsor reserves the right to close the trial site or terminate the trial at any time for any reason at the sole discretion of the sponsor.

In addition, the investigator may initiate trial-site closure at any time, provided there is reasonable cause and sufficient notice is given in advance of the intended termination. Reasons for the early closure of a trial site by the sponsor or investigator may include, but are not limited to:

- Failure of the investigator to comply with the protocol, the requirements of the independent Ethics Committee (IEC)/Institutional Review Board (IRB) or local health authorities, the sponsor's guidance documents/trial plans, ICH GCP E6(R2), and applicable regulatory requirements.
- Inadequate recruitment of subjects by the investigator
- Discontinuation of further investigational medicinal product (IMP) development

The sponsor may, based on available data, need to discontinue further development of GEN1044. If the development of the GEN1044 is discontinued and trial termination is necessary, the sponsor will make their best effort to provision post-trial access of GEN1044 for those ongoing trial participants with a potential treatment benefit, in accordance with local laws and regulations.

Version: 4.0

# 5 TRIAL POPULATION(S)

#### 5.1 Inclusion Criteria

Each potential subject must fulfill all of the following criteria to be assigned to treatment in the trial.

#### For Dose Escalation:

1. Subject with locally advanced or metastatic solid tumor(s) (excluding subjects with primary central nervous system [CNS] tumors), who has experienced disease progression while on standard therapy or is intolerant of, or not eligible for, standard therapy.

# For Expansion:

- 1. Criterion modified per Amendment 3.
  - 1.1 Subject must have an advanced or metastatic, pathologically confirmed diagnosis of one of the following tumors:
    - a. **Uterine Cancer:** Subject with advanced or metastatic uterine cancer (excludes uterine sarcoma, carcinosarcoma of uterus [including malignant mixed mullerian tumor], endometrial leiomyosarcoma and endometrial stromal sarcomas) for whom non-hormonal systemic therapy is required. Subject must have progressed on or after a prior systemic, platinum-based chemotherapy regimen administered for her advanced, recurrent, or metastatic disease. **Note:** Platinum-based regimens administered in the adjuvant or neoadjuvant setting are not included as a prior regimen. Subject should have received no more than 3 systemic regimens in the recurrent/metastatic setting.
    - b. **Prostate Cancer:** Subject with advanced or metastatic, histologically-confirmed adenocarcinoma of the prostate. Subject must be castration resistant (defined as testosterone ≤50 ng/dL, or history of bilateral orchiectomy) and have progressed on at least 1 taxane-based chemotherapy regimen AND at least 1 androgen synthesis inhibitor (ASI) (eg, abiraterone, enzalutamide, apalutamide). Subject should have received no more than 4 systemic regimens in the recurrent/metastatic setting.
    - c. **Esophageal Cancer:** Subject with locally advanced or metastatic adenocarcinoma or squamous cell carcinoma of the esophagus OR advanced/metastatic Siewert type I adenocarcinoma of the esophagogastric junction (EGJ), who progressed on or after at least 1 but no more than 3 prior lines of systemic treatment(s) for advanced disease. Subjects with HER2/neu positive esophageal cancer are required to have received treatment with an approved HER2/neu targeted therapy.
    - d. **Triple Negative Breast Cancer (TNBC):** Subject with locally advanced or metastatic TNBC (defined as HER2-negative with <1% of tumor cell nuclei immunoreactive for estrogen receptor (ER) and progesterone receptor per local assessment) who has progressed during or after at least 1 but no more than 3 systemic therapies (including a taxane in the metastatic or recurrent setting).
    - e. Squamous Cell Carcinoma of the Head and Neck (SCCHN): Subject with recurrent/metastatic squamous cell carcinoma of oral cavity, oropharynx, paranasal

Version: 4.0

sinuses, nasal cavity, hypopharynx, or larynx. Subject must have received prior therapy with a platinum-based regimen AND anti-PD-1/PDL1, if eligible for such therapy. Subject eligible to receive anti-EGFR therapy must have received anti-EGFR therapy prior to study entry. Subject should have received no more than 3 systemic regimens in the recurrent/metastatic setting. **Note:** Prior therapy administered in the neoadjuvant or adjuvant setting is not considered a systemic regimen.

- f. Non-small Cell Lung Cancer (NSCLC)/ACC and NSCLC/SCC: Subject with locally advanced or metastatic adenocarcinoma (ACC) or squamous cell carcinoma (SCC) of NSCLC must have experienced disease progression on or after his/her most recent systemic therapy for locally advanced or metastatic disease. Subject must have received prior therapy with a platinum-based regimen; a tyrosine kinase inhibitor (TKI) for the following mutations: anaplastic lymphoma kinase (ALK), c-ros oncogene 1 (ROS1) gene rearrangement or EGFR mutation; AND anti-PD-1/PDL1 if eligible for such therapy. Subject should have received no more than 3 systemic regimens in the locally advanced or metastatic setting. Note: Although the same criteria are relevant, NSCLC/ACC and NSCLC/SCC will be assessed in separate subject cohorts.
- g. Bladder Cancer: Subject with locally advanced or metastatic urothelial carcinoma (of the bladder, ureter, urethra, or renal pelvis) who has disease progression during or following his/her most recent systemic therapy for locally advanced or metastatic disease. Subject must have a received prior therapy with a platinum based regimen and anti-PD-1/PDL1 if eligible for such therapy. Subject should have received no more than 3 systemic regimens in the locally advanced or metastatic setting. Note: Prior therapy of neoadjuvant or adjuvant setting is not considered a systemic regimen.

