In addition to the above mitigation strategies against the potential risk of CRS, multiple safety groups including the Dose Escalation Committee (DEC), independent Data Monitoring Committee (DMC) and the sponsor Safety Committee (SC) will be reviewing data from this trial. Given the potential for enhanced benefit with limited and manageable toxicity indicates that GEN1044 should be administered in subjects of high unmet need including patients with solid malignancies who have progressed on all available SOC therapies and are otherwise ineligible to receive these. All subjects enrolled in this trial will be monitored by qualified health care professional(s) who will provide care and evaluate the subject's response to the trial drug, in terms of its safety and efficacy. In totality, the benefit-risk ratio is considered positive for this FIH, phase 1/2 trial of GTC1044-01. For more comprehensive information related to the nonclinical studies, potential safety aspects and the known and expected benefits/risks for GEN1044, refer to the Investigator's Brochure.

Version: 4.0

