## 11.6.3 Statistical Hypothesis, Model, and Method of Analysis

No formal statistical hypotheses are formulated in this trial. Any P-values will be considered as hypothesis generating results to be considered for future trials.

The estimated ORR and the exact 2-sided 95% confidence intervals (CIs) using the Clopper-Pearson method will be presented for each expansion cohort. Individual subject data listings will be provided.

The maximal response (maximal reduction in the sum of the longest diameter in the target lesions) in target lesions at any time on trial will be reported using waterfall plots.

The results of the response as seen in the escalation part will be reported similarly.

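### The SCCHN expansion criterion alone has no progression wording, so residual effect of prior therapy could count towards ORR, DCR and PFS

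*Protocol*

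**What the plan says.** Protocol Section 5.1, For Expansion, sets a prior-therapy condition for each tumor type:

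- **SCCHN (1.1e):** "Subject must have received prior therapy with a platinum-based regimen AND anti-PD-1/PDL1, if eligible for such therapy". It adds: "Subject eligible to receive anti-EGFR therapy must have received anti-EGFR therapy prior to study entry". There is a cap of three systemic regimens. Progression is not mentioned, and the synopsis (Section 1.1) gives the same text.
- **NSCLC, both cohorts (1.1f):** the subject "must have experienced disease progression on or after his/her most recent systemic therapy for locally advanced or metastatic disease".
- **Bladder (1.1g):** a subject "who has disease progression during or following his/her most recent systemic therapy for locally advanced or metastatic disease".
- **Uterine (1.1a):** "Subject must have progressed on or after a prior systemic, platinum-based chemotherapy regimen administered for her advanced, recurrent, or metastatic disease".
- **Prostate (1.1b), esophageal (1.1c), TNBC (1.1d):** progression on at least one taxane regimen and at least one androgen synthesis inhibitor (prostate), or on at least one prior systemic line or therapy (the other two).

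The criteria common to both parts do not mention progression on prior therapy. The progression wording in criterion 1 for Dose Escalation applies to that part only. Section 2.3 refers to "patients with solid malignancies who have progressed on all available SOC therapies", but as a group included among subjects of high unmet need.

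Exclusion 3.1b sets the washout of an anti-cancer agent at the shorter of 28 days and five half-lives. Section 9.2.1.1 allows the baseline scan from Day -28. Appendix 2 measures partial response against the baseline sum of diameters. Section 11.5.10 counts any confirmed CR or PR by local review towards ORR, and adds SD for DCR.

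**The concern.** In an uncontrolled cohort, tumor shrinkage can be credited to GEN1044 only if it is unlikely that the tumor would have shrunk without it. Progression on the last regimen is the usual support for that. Criterion 1.1e does not ask for it.

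The route to bias has three steps. A subject stops a prior agent while still benefiting. The baseline scan is taken within 28 days before C1D1, possibly inside the washout. Any further shrinkage is then read against that baseline, and nothing in the endpoint definition separates continuing effect of the earlier drug from effect of GEN1044.

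At stake are the SCCHN futility and success calls, which use a low bar (5/40 against a historical rate of 10%), and the interpretation of DCR and PFS. The only SCCHN response rates in the protocol's background (Section 2.1.1.5: 13.3% and 5.8%) come from patients who had progressed after platinum. The protocol does not say whether its 10% benchmark rests on them.

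**Working it through.** **Step 1. Which cohorts require progression, and on what?** Of the eight planned cohorts:

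- Three tie progression to the most recent therapy: NSCLC/ACC, NSCLC/SCC and bladder.
- Four require progression on some prior therapy, not explicitly the latest: uterine, prostate, esophageal and TNBC.
- One has no progression wording: SCCHN.

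**Step 2. Does anything else supply it for SCCHN?** Recurrent or metastatic describes disease state. Measurable disease is compatible with an ongoing partial response. Exclusion 7 is a case-by-case judgement that does not name progression. None of these is a progression requirement.

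**Step 3. Reproduce the plan's figures (Section 11.7, Tables 19 and 20, Case A).** Inputs: p0 = 10%, prior Beta(1.1, 1.9), maximum n = 40, interim at about 20, success if the posterior P(ORR > p0) is at least 70%, futile if the predictive probability of success is below 10%.

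- Posterior P(ORR > 10%) is 0.607 at 4/40 and 0.775 at 5/40, so success needs 5/40, as stated.
- Predictive probability is 0.022 at 0/20 and 0.156 at 1/20, so one responder is enough to continue.
- At a true ORR of 10%, the chance of stopping is 0.9^20 = 12.2%. Given continuation, estimated ORR reaches p0 in 63.8% and success in 41.6%. Table 20 gives 12%, 64% and 41%. The plan's arithmetic is sound.
- Not conditional on continuing, success is 36.6%; ignoring the interim it is P(Bin(40, 0.10) ≥ 5) = 37.1%. The interim matters little here and is ignored in Step 4.

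**Step 4. Effect of a few non-progressed subjects.** Let k of the 40 be non-progressed, each with probability q of a confirmed response, and let the other 40 − k respond with probability 0.10. Then

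P(at least 5) = Σ over j = 0..k of C(k, j) q^j (1 − q)^(k−j) × P(Bin(40 − k, 0.10) ≥ 5 − j).

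Both k and q are assumptions; the documents give neither.

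- k = 0: 0.371.
- q = 0.10: still 0.371 for any k, because all 40 then share the same rate.
- q = 0.30, k = 1: 0.7 × 0.350 + 0.3 × 0.556 = 0.412.
- q = 0.30, k = 2: 0.49 × 0.330 + 0.42 × 0.535 + 0.09 × 0.746 = 0.454.
- q = 0.30, k = 3: 0.343 × 0.310 + 0.441 × 0.514 + 0.189 × 0.730 + 0.027 × 0.896 = 0.495 (0.4947 before rounding, so 49%).
- q = 1 (worst case), k = 1, 2, 3: P(Bin(39, 0.10) ≥ 4) = 0.556; P(Bin(38, 0.10) ≥ 3) = 0.746; P(Bin(37, 0.10) ≥ 2) = 0.896.

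**Step 5. The same question as a share of the cohort, with the interim applied.** If a share f has response probability q, the apparent ORR is (1 − f) × 0.10 + f × q. With q = 0.30, f = 10% gives 12% and f = 20% gives 14%. Success given continuation rises from 42% to 57% and 70%.

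**The case against.** The best reply has four parts.

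**SCCHN is not uniquely exposed.** A reader might infer from the missing wording that this cohort alone admits carry-over and cannot be compared with the other seven. The documents do not support that. A subject who progressed on one line and is responding to a later one literally satisfies the uterine, prostate, esophageal and TNBC criteria. SCCHN is the only criterion with no progression wording, and the gap is widest there, but a lesser form exists in those four.

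**Stability is not response.** A reader might also infer that stable subjects inflate the primary endpoint. They do not: ORR needs a confirmed 30% decrease after the trial baseline, and shrinkage before that scan does not count. Stable subjects can affect DCR and PFS only.

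**Section 2.3 does not define the population.** It lists progressed patients as included among those of high need. It indicates intent and does not establish a contradiction.

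**There are safeguards.** Exclusion 7 allows a subject to be refused if a condition could confound assessments. Section 9.1.5 records best response, reason for stopping and progression dates for prior therapies, so non-progressed subjects could be identified. The futility rule is non-binding, the sponsor's Safety Committee looks at all the data, and Section 11.6.3 states "No formal statistical hypotheses are formulated in this trial". SAP Section 2.2 reports that no expansion data were collected.

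All of this stands as a limit on impact. None of it puts a progression requirement into 1.1e.

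**Conclusion.** The gap in the text is real: SCCHN subjects still responding to or stable after prior therapy are eligible under the protocol as written, and a confirmed post-baseline response in such a subject would count as a GEN1044 response.

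The direction of bias is upward if these subjects are more likely than 10% to have a confirmed response without any added drug effect; the size is unknown. With one to three of them and an assumed 30% response chance, the probability of meeting the success bar at a true ORR of 10% moves from 37% to between 41% and 49%. A reader might take 56% to 90% as the effect of merely enrolling one to three such subjects. That range holds only if each is certain to have a confirmed response, which nothing in the documents supports; it is an upper bound for those counts.

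This is a design weakness in the protocol, relevant if the criterion is reused. It does not bear on any reported result.

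**What to change.** In 1.1e, and in the matching synopsis text, add the progression condition already used in 1.1f and 1.1g, adapted to the recurrent/metastatic setting: progression on or after the most recent systemic therapy. At the same time, check whether 1.1a to d should also refer to the most recent therapy, so that the entry condition is the same across cohorts.

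The cost is one sentence in each of two places. The practical downside is that a few subjects who stopped prior therapy without progression, for example for intolerance, could not enter until they progress.
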